The 20 HD facilities will be randomized to the four intervention combinations of the 2x2 factorial design, assigning 5 facilities to each of the 4 combinations (both provider education and patient activation using peer mentoring; provider education alone; patient activation alone; and neither intervention). Facilities will be stratified by geographic region and possibly socio-economic status to ensure treatment balance on those factors.

X. Primary and Secondary Outcomes

- Primary Outcome:
 - Dialysis session stability (Intradialytic hypotension)
- Secondary outcomes:
 - Fluid adherence (Interdialytic Weight Gain)
 - Dialysis adherence
 - Patient symptoms
 - Quality of Life
 - Hospitalization
 - Mortality
- Behavioral Outcomes
 - Patient Involvement in Dialysis Session Stability
 - Fluid Management Practice Patterns Measure (Providers)

XI. Data Collection Methods

Please refer to the attachment entitled "Data Elements List" for a detailed list.

a) Data for the following outcomes **are gathered as part of the standard workflow at hemodialysis facilities**, and will be electronically transferred from FMCNA to UM's Kidney Epidemiology and Cost Center for analyses:

- Intradialytic hypotension (primary outcome)
- Interdialytic weight gain
- Patient symptoms during the dialysis session based on patient reports of their physical experiences and sensations, recorded in the digital Chairside documentation system
- Health-related quality of life

- Hospitalizations
- Fluid practice patterns measure components: post-dialysis target weights, treatment time delivered, ultrafiltration rate, patient medications, use of cool dialysate
- Mortality
- Change in treatment modality for a patient

The FKC ID1 and FKC ID2 unique patient identifiers will be used to link data clinical patient and session data, and data from peer mentoring received from the peer mentoring management system (PMMS).

3) Data for the following outcome is not part of the standard workflow at hemodialysis facilities, but **will be gathered electronically (via 2 questions added to the FMCNA Chairside application) by staff as part of the routine workflow while facilities are in the study** (these data will also be electronically transferred):

- Patient symptoms after the session in the form of recovery time
- Patient fluid removal goal requests

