11.4 FINAL ANALYSIS PLAN

Aim 1. Test and conduct a cluster-randomized controlled trial (CRCT) to compare the effects of the above HD facility-level interventions on the primary outcome of dialysis

session stability over an intervention period of 24 weeks and a post-intervention follow-up period of 12 weeks.

Preliminary data analysis. We will compare the four randomized groups to assess covariate balance on participant characteristics, such as demographics. This analysis will test for potential selection bias that might lead to confounding of study results. If study arms are found to be imbalanced on baseline characteristics, in addition to those specified in the analyses below, these characteristics will be included in the regression models as a sensitivity analysis.

Analysis of Primary Outcome. For Aim 1, the outcome is a dichotomous measure of HD stability, where an unstable session is defined as the dialysis session stability, where an unstable session is defined as SBP falling below 100 when the starting SBP was ≥ 100 . This outcome will be collected through digital records for all HD sessions of all patients at each facility during the study period. The analysis will be done in two ways. First, as a continuous variable, as described in the power analysis. Using individuals with a minimum of 60 dialysis sessions, the proportion of unstable sessions will be computed. Linear mixed models will be employed to compare individuals in facilities in the two treatment arms to individuals in the non-intervention facilities. Random effects for facility clustering will be accounted for using the MIXED procedure in SAS. As a sensitivity analysis, dialysis session stability will also be examined as a yes/no variable and analysis will be carried out on the longitudinal dataset using logistic regression with a random effect for both patients and facilities, using the GLIMMIX procedure in SAS. The random effects will model the correlations among the measurements at each level. This analysis will use data from all patients, not just those with at least 60 dialysis sessions.

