For the above analyses, the variables of primary interest are the main effects of the interventions. *Session-level* covariate adjustment will include: (1) weekday of session, (2) dialysis session shift, (3) average session blood flow rate; (4) average session dialysate flow rate, and (5) dialysate composition (sodium, potassium, magnesium). *Patient-level* covariate adjustment will comprise: (1) patient demographics (age, race, ethnicity, sex, employment, literacy, education level, language spoken); (2) time since first dialysis; (3) cause of ESRD, (4) treatment history; (5) total transplants; (6) vascular access type; (7) patient laboratory data (serum phosphorous, dialysis adequacy, anemia management (hemoglobin), iron indices (serum ferritin, serum iron), mineral metabolism indices (calcium, phosphate, PTH)); (8) comorbidity index; (9) individual comorbidities and comorbidities in combination, including COVID-19; (10) patient's heart rate variability (based on variability in heart rate (HR) during dialysis session (difference between the highest and lowest heart rates, standard deviation of the heart rate measures, the square root of the mean squared differences of successive heart rate measures); (11) patient medications (prescriptions medications administered outside of center or in-center (including ESA prescription, iron, antibiotics and vitamin D analog), and non-in-center prescriptions). Patient data will be censored while they are at COVID-19 isolation facilities. Regression diagnostics will be used to assess model fit. Checks for functional form of continuous adjustment covariates will be carried out and any transformations will be implemented prior to adding the intervention variables to the model.

Three secondary analyses are planned for this Aim. The first will test the treatment effects in a similar model but adding adjustment for any covariates found to be unbalanced between treatment groups in preliminary analyses. This has the ability to further adjust for important confounders of treatment effects, but because it will use data-driven covariate decisions that are subject to analysis bias, it will be interpreted with caution. The next secondary analysis will test the interaction between the two interventions to detect a possible synergistic or antagonistic

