effect. (Further discussed in the heterogeneity of effects section). Although the study is not powered to detect even moderate interaction effects, it is possible that a strong interaction could be detected, and such an effect would be of interest.

The primary results will be based on the treatment effects tested in the initial models described for cluster-randomized trials with pre-planned covariates. Intent-to-treat analyses will be carried out, so that any deviations from the randomized interventions will not be taken into account in the primary test of treatment effects. Additionally, we will conduct as-treated analyses for the peer mentoring intervention whereby only patients who received peer mentoring are compared to patients in the other treatment arms, with adjustment for the same factors as in the intent-to-treat analyses. The small number of facilities (20) will preclude post-hoc adjustment for facility non-compliance with the interventions.

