In both Aims 1 and 2, the primary results will be based on the treatment effects tested in the initial models described for CRCTs with pre-planned covariates. Depending on the specific outcome, covariate adjustment for these analyses will include: (1) patient demographics (age, race, ethnicity, sex, employment, literacy, education level, language spoken), (2) time since first dialysis, (3) cause of ESRD, (4) treatment history, (5) total transplants, (6) vascular access type, (7) patient laboratory data (serum phosphorous, dialysis adequacy, anemia management (hemoglobin), iron indices (ferritin, serum Iron), mineral metabolism indices (calcium, phosphate, PTH)); (8) comorbidity index; (9) individual comorbidities and comorbidities in combination, including COVID-19; (10) patient's heart rate variability for the whole session or up until IDH occurs (if IDH occurs) (based on variability in heart rate (HR) during dialysis session (Difference between the highest and lowest heart rates, standard deviation of the heart rate measures, the square root of the mean squared differences of successive heart rate measures)); and (11) patient medications (prescriptions medications administered outside of center or in-center (including ESA prescription, iron, antibiotics and vitamin D analog)). Intent-to-treat analyses will be carried out, which means that any deviations from the randomized interventions will not be taken into account in the primary test of treatment effects. Additionally, we will conduct as-treated analyses for the peer mentoring intervention whereby only patients who received peer mentoring are compared to patients in the other treatment arms, with adjustment for the same factors as in the intent-to-treat analyses. The small number of facilities (20) will preclude post-hoc adjustment for facility non-compliance with the interventions.

Heterogeneity of Treatment Effect Analyses (Moderation). As with the primary outcome analyses, the following potential moderators will be assessed: 1) patient demographics, including age, race, ethnicity, literacy, and education level; (2) comorbidities; and (3) heart rate variability.

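### The primary models adjust for in-session heart-rate variability and patient medications with no baseline window, and one covariate list lets the heart-rate window end at the outcome

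*Combined protocol and SAP*

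**What the plan says.** Section 11.4 gives two lists of adjustment covariates.

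- **Analysis of Primary Outcome (Aim 1).** Patient-level item 10 is "heart rate variability (based on variability in heart rate (HR) during dialysis session", with three measures: "difference between the highest and lowest heart rates, standard deviation of the heart rate measures, the square root of the mean squared differences" of successive readings. Item 11 is "patient medications (prescriptions medications administered outside of center or in-center", ending with a clause for prescriptions that are not given in the centre. Neither item has a measurement period.
- **Aim 2 text, covering both Aims.** The same items recur, but item 10 is now "heart rate variability for the whole session or up until IDH occurs (if IDH occurs". Again no period is given.

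Both places make these the primary models. The Aim 1 text says "The primary results will be based on the treatment effects tested in the initial models", with pre-planned covariates and an intent-to-treat analysis. The Aim 2 text says "In both Aims 1 and 2, the primary results will be based on the treatment effects tested in the initial models".

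Elsewhere the protocol treats blood-pressure medication as something the interventions may alter. Changes in it are a component of the fluid practice patterns measure, described as practices the interventions could change (3.2.3). The checklist prompts review of drugs that affect blood pressure (2.2.1). The number and categories of such drugs are a listed mediator of the primary outcome (11.4, Mediators of the Primary Outcome). Section 7.2 says that 12 weeks of baseline data are collected retrospectively for every clinic.

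**The concern.** Adjusting for baseline covariates leaves the target of estimation intact. Adjusting for a variable measured after randomisation may not: if the intervention changes it, part of the effect is removed, and if the outcome shapes it, the model conditions on a proxy for the outcome.

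Both routes are open here. If heart-rate variability comes from on-study sessions and its window ends at IDH, an unstable session contributes fewer readings than a stable one, so the covariate carries information on the outcome. If on-study medications include blood-pressure drugs, the total-effect model adjusts for a variable that the plan elsewhere calls a mediator. The result would be reported as intent-to-treat but need not be the total effect of assignment for which Table 5 is powered.

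**Working it through.** **1. The two lists side by side**

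| | Aim 1 list | List for both Aims |
|---|---|---|
| Heart-rate window | during the session, no cut-off | whole session, or up to IDH |
| Medications | in-centre and outside, plus a closing clause on non-in-centre prescriptions | in-centre and outside, without that clause |
| Measurement period | none | none |
| Applies to | Aim 1 | both Aims, depending on the outcome |

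An analyst cannot tell which list governs, or whether baseline or on-study values are meant.

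**2. The plan's own power figure.** Inputs from 11.2: 10 facilities per group, 60 patients each, ICC 0.10, alpha 0.05 (taken as two-sided).

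- Design effect = 1 + 59 × 0.10 = 6.9; effective n per group = 600 / 6.9 = 86.96.
- Power = Φ(D / (SD × √(2/86.96)) − 1.96). For D = 0.034 and SD = 0.08: 0.034 / 0.01213 = 2.80, and Φ(0.84) = 80.0%.
- The other three columns give 61.1%, 90.9% and 80.9%. Table 5 has 80%, 61%, 91% and 81%, so it reproduces.

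**3. Why the cut-off matters.** For independent normal readings the expected range is 2.97 SD over 9 readings, 2.33 over 5 and 1.69 over 3. Fewer IDH sessions therefore mean longer windows and larger ranges. The sample SD depends much less on the number of readings. Range and SD together thus nearly recover how many readings were cut off, which is close to recovering the outcome.

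**4. Illustration.** From the documents: 2×2 design, 20 facilities × 60 patients × 60 sessions, IDH 20%, D = 0.034, SD = 0.08, ICC = 0.10, four-hour sessions (12 hours over three sessions a week, 2.1.3). Assumed: readings every 30 minutes (9 per session), independent or autocorrelated at 0.5; between-patient CV of heart-rate SD 0.1 or 0.3; heart rate unrelated to IDH and to treatment; window ends at IDH. Each measure is averaged per patient and entered in a random-intercept model. The ratios below are adjusted to unadjusted effect.

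| On-study covariates | IDH from hour 1 | IDH from hour 2 | IDH in last hour only |
|---|---|---|---|
| All three measures | 0.63-0.67 | 0.81-0.82 | 0.95 |
| Implied estimate (0.034 × ratio) | 0.021-0.023 | 0.027-0.028 | 0.032 |

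- Range and SD without the third measure: 0.64-0.70 with IDH from hour 1, so this pair drives the result.
- One measure alone: range 0.98-1.00; SD 1.00; successive differences 1.00.
- Three measures from 36 baseline sessions: 0.998-1.004.
- Power: 75-81% with the three on-study measures, 79-88% with baseline measures, 77-81% unadjusted.

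A second simulation used other settings: range only, 8 readings, D = 0.040, 72 sessions, IDH possible from the second reading. The estimate moved from 0.0386 to 0.0289 (25% smaller) when patients did not differ in heart-rate variability, from 0.0392 to 0.0366 (7%) with moderate differences, and from 0.0374 to 0.0367 (2%) with larger ones. Baseline values, or no cut-off, gave no shrinkage.

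**5. Late entrants.** Sixty sessions at three a week take 20 weeks. Only patients joining in the first 4 weeks (if 24 weeks count) or the first 16 (if 36 count) can reach the linear model. Turnover of 15-20% (5.4.1) is 180-240 of 1,200. Spread evenly over 48 weeks, that gives 180 × 4/48 = 15 to 240 × 4/48 = 20 patients, or 180 × 16/48 = 60 to 240 × 16/48 = 80.

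**The case against.** The best defence is that a baseline trait was meant. The preliminary-analysis paragraph speaks of arms "imbalanced on baseline characteristics, in addition to those specified in the analyses below", which can be read as calling the listed covariates baseline ones. Heart-rate variability is filed as a patient-level item, is listed as a moderator beside age, race and education for both Aims, and appears in no mediator list. A reader might infer that the plan expressly adjusts for on-study values; the documents do not support that, because the period is simply missing. What does not fit the baseline reading is the window ending at IDH. Stopping there does have a purpose, since it excludes heart-rate changes caused by IDH or its treatment, but that purpose does not require on-study values in the primary model.

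The medication argument is inferential. Item 11 names ESA, iron, antibiotics and vitamin D, and the plan uses a separate term for blood-pressure drugs when it lists them as a mediator. Section 4.1 does use item 11's own term in "Fluid practice patterns measure components: post-dialysis target weights, treatment time delivered, ultrafiltration rate, patient medications, use of cool dialysate", but that is a list of data sources and does not show that the variables are the same. What stands is that item 11 is broad enough to include blood-pressure drugs and does not exclude them.

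A reader might also infer that mediation step 3 fails. Section 11.4 does not say that these covariates are carried into that step. Nor is harm shown for laboratory values, COVID-19, or session flow rates and dialysate composition. The session-level logistic model is in any case a sensitivity analysis.

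**Conclusion.** The point holds as a gap in the specification of the primary models. Two covariates lack a time point, the two lists disagree, and one wording lets the outcome define a covariate. It should be fixed before analysis, because choosing the window after seeing results would be a post-hoc choice of primary model.

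The true size cannot be derived from the documents. A reader might take the 33-37% shrinkage as the expected bias. It is an extreme: it needs on-study values, the cut-off, IDH possible from the first hour, and range and SD in the model together. The plan does not say whether the three measures are alternatives or are all to be entered. A single measure gives about 0-2% at between-patient CVs of 0.1-0.3, and more than that for the range only if patients hardly differ in heart-rate variability. Real heart-rate changes before IDH could move the estimate either way. Under these assumptions the harm is a misstated effect size more than lost power. No size is claimed for medications, since the documents give no mediated share.

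**What to change.** In the primary models for Aims 1 and 2:

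- Define heart-rate variability and medications, including any blood-pressure drugs, from the 12-week baseline.
- Delete the window ending at IDH from the primary covariate list.
- Make the two lists in 11.4 identical, and state whether item 11 includes blood-pressure drugs.
- Keep on-study heart-rate variability and blood-pressure medications for mediation or supplementary models.
- For patients who enter after the intervention starts, use a missing-value indicator or the multiple imputation already named under Missing Data Issues. Values at clinic entry are not a substitute: they are post-randomisation, and in provider-intervention clinics the checklist is meant for every session (6.2.1).

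The cost is wording in the analysis plan; no new data are needed. The downside is a small loss of precision where concurrent values would predict better, and imputed or flagged values for the late entrants counted above.

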One problem with limiting the focus of this trial to only this comparison (as in a simple two-arm trial) is that if the two interventions were found to be equally effective, there would be no way to determine whether either represented an improvement over standard care. Without a control group, changes in the intervention groups compared to baseline could be attributed to secular trends. Because we have a control group in our design, we can rule out (or confirm) secular trends; therefore, when paired with tests i and ii above, we are able to determine simultaneously that one intervention is both: 1) better (or not) than standard care, and 2) equivalent (or not) to the other intervention.

- iv. Are there synergistic or antagonistic effects between the provider education and peer mentoring interventions?
 - a. The purpose of this test is to determine whether the effect of one intervention differs depending on the presence of the other intervention. The test compares:
 - [Cells ((A-C) – (B-D))] – F test comparison to examine the effects of provider education intervention with and without the presence of the patient activation intervention.
 - This is equivalent to ((A-B) – (C-D)), which examines the patient activation intervention with or without provider education.

This interaction test will provide power to detect strong synergistic or antagonistic effects.

The use of factorial designs in clinical trials is widely accepted, and is discussed, for example, in a well-known book on clinical trials.¹⁴⁵ Two particular advantages of factorial designs mentioned in this book are the **gain in efficiency** (the ability to test two treatments using the same number of subjects ordinarily used to test a single treatment) and the **ability to test for interaction** between treatments. This statistically efficient approach is valuable for health care interventions, where rigorous evaluation is typically expensive.¹⁴⁶

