The third will be a secondary analysis of patient proportion with IDH before versus after the intervention phase to test whether the intervention effects are maintained. The basic analysis is a paired comparison of % IDH pre- versus post-intervention, with a few necessary adjustments. First, because the intervention phase will span 24 weeks and the maintenance phase will span only 12 weeks, the variance of the percent IDH will differ between periods. We will address that by using a mixed model with heterogeneous variance. This strategy will work for the situation of full duration of each patient's participation (24 weeks plus 12 weeks). If there are enough patients who enter or exit during either period, we will do a similar analysis, but use patient-and phase-specific weights to adjust for differing variances. Second, there may be carry-over effects after the intervention phase that only last for a few weeks. We will test that possibility by classifying the 12 weeks of the post-intervention phase as separate one-month periods, and testing whether the monthly post-intervention IDH percentages are individually different from the intervention phase IDH percentages. Testing for a decreasing trend during the maintenance period will also be performed. Third, these analyses will be carried out separately among the four groups (provider training/checklist alone; peer mentoring alone; both interventions together, and neither intervention). A joint analysis may also be performed to test for additive or interactive effects.

Missing Data Issues (MD-1). Because ours is an educational intervention with support from the dialysis facility's parent organization, we expect facility attrition to be very low. Nevertheless, if facilities do drop out during the intervention phase, they will be replaced and the intervention will take place at a new facility. A facility would need to be replaced if: 1) they request to leave the study; or 2) 75% of the staff do not complete the training within the first 14-16 weeks of the intervention period.

As for missing outcome data for facilities in the study, data for our primary outcome as well as two secondary outcomes (fluid adherence/Interdialytic weight gain and dialysis session adherence) are gathered at the dialysis session level, using data that are automatically gathered when treatment is delivered.

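### Maintenance of effect is judged within each of the four groups, with no required contrast against the control group's change, so shared calendar drift stays in every estimate

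*Combined protocol and SAP*

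**What the plan says.** Section 11.4 gives the purpose of the third secondary analysis as "to test whether the intervention effects are maintained". Its starting point is within-patient: "The basic analysis is a paired comparison of % IDH pre- versus post-intervention, with a few necessary adjustments". Three elements follow.

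- A mixed model with unequal variances, because "the intervention phase will span 24 weeks and the maintenance phase will span only 12 weeks".
- A carry-over check by "testing whether the monthly post-intervention IDH percentages are individually different from the intervention phase IDH percentages", plus a trend test within the maintenance period.
- A statement that "these analyses will be carried out separately among the four groups". The group receiving neither intervention is one of the four.

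The only between-group element is "A joint analysis may also be performed to test for additive or interactive effects".

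The text moves between comparators: before against after the intervention phase, and intervention phase against maintenance phase. The contrast that defines maintenance is never fixed.

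Section 4.1, under the factorial design, explains why the trial has a control group at all: "Without a control group, changes in the intervention groups compared to baseline could be attributed to secular trends". Section 4.1, under trial periods, also says the design takes care of temporal variability from the staggered start. The covariates listed in section 11.4 contain no calendar-time term.

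**The concern.** An intervention effect in this trial is a difference from the groups without that intervention. Whether it is maintained is therefore also a question about a difference. A change measured inside one group cannot separate a fading or persisting effect from movement that would have happened anyway.

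Such movement is plausible here. Table 2 (section 4.1) gives estimated data-collection end dates of 30 September or 31 October for all five implementation groups. If follow-up is the last 12 weeks, it starts about 8 July or 8 August, so follow-up falls in roughly July to October in every arm. Staggering the start does not separate season from phase. Each implementation group does hold one facility from each arm, so a between-arm contrast would cancel drift that the arms share.

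Section 3.1 puts the 12-week follow-up inside Aim 1, and section 4.1 presents the durability of effect as one of the trial's useful products. A misleading maintenance result would bear directly on that.

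**Working it through.** **1. The plan's own figures.** Inputs from section 11.2: 60 patients per facility, 10 facilities per side, ICC 0.10, SD 0.08 or 0.10, alpha 0.05 (taken as two-sided).

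- Design effect = 1 + (60 − 1) × 0.10 = 6.9; effective n per side = 600 / 6.9 = 86.96.
- SE = SD × √(2 / 86.96) = 0.0121 (SD 0.08) or 0.0152 (SD 0.10).
- Power = Φ(D / SE − 1.96) = 0.800, 0.611, 0.909 and 0.809, against 80%, 61%, 91% and 81% in Table 5.

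Table 5 reproduces. It concerns the between-arm comparison, which is not in dispute. No power is given for the maintenance analysis.

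**2. What each estimate measures.** Let d be the drift common to all facilities and L the true change in the intervention effect.

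- Change within an intervention group = L + d.
- Change within the no-intervention group = d.
- Difference between the two = L.

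With d = +2.0 points and L = 0, the within-group estimate is +2.0 and the contrast is 0. With L = +3.4 (an effect lost) and d = −3.4, the within-group estimate is 0 and the contrast is +3.4.

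**3. How much drift would mislead.** For one group (5 facilities, 300 patients), with facility autocorrelation c and within-patient correlation r between phases:

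Variance of mean change = 2 × ICC × SD² × (1 − c) / 5 + 2 × (1 − ICC) × SD² × (1 − r) / 300.

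The documents give neither c nor r; the assumed ranges are c = 0.5 to 0.95 and r = 0.5 to 0.8. The formula also applies the planning SD to both phases.

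- Most precise case (SD 0.08, c 0.95, r 0.8): 0.0000128 + 0.0000077 = 0.0000205; SE = 0.0045.
- Least precise case (SD 0.10, c 0.5, r 0.5): 0.000200 + 0.000030 = 0.000230; SE = 0.0152.

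Drift at which the expected change equals the critical value:

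- Normal test, 1.96 × SE: 0.9 to 3.0 points.
- t test with 4 df, 2.776 × SE: 1.3 to 4.2 points.

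**4. Rejection rates when the effect has not changed (L = 0).**

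| Common drift | Within group, t (4 df) | Within group, normal | Between-group contrast |
|---|---|---|---|
| 0 | 5% | 5% | about 5% |
| 1 point | 8–39% | 10–60% | about 5% |
| 2 points | 18–90% | 26–99% | about 5% |
| 3 points | 33% to nearly 100% | 51% to nearly 100% | about 5% |

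The contrast column comes from 20,000 simulated trials in each of two settings (SD 0.08, c 0.8, r 0.8; SD 0.10, c 0.8, r 0.5), with results between 4.7% and 5.2%.

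**5. The reverse error.** In the same two settings, a 3.4-point loss offset by 3.4 points of downward drift is flagged by the within-group test in about 5% of trials. The contrast finds it in 52–79% (one group against control) or 86–99% (10 against 10 facilities).

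**The case against.** The strongest reply is that the no-intervention group receives the identical analysis, so common drift would be estimated and seen, and section 4.1 says the control group will be used to rule secular trends in or out. That stands in part: the drift would not be hidden. But setting four separate within-group results beside each other is not a test of their difference, and section 11.4 does not require the subtraction. The optional joint analysis could contain the right contrast, but it is neither required nor framed as a maintenance test.

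Four stronger readings are tempting and are not supported.

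- *The plan takes a non-significant monthly test as proof of maintenance.* Section 11.4 never says so. It presents the monthly tests as a check for short-lived carry-over.
- *No randomised comparison covers follow-up.* Aim 1 is to test and compare the interventions over both periods, and the between-arm models in section 11.4 use outcomes from the study period. Their time window is not pinned down, but follow-up is not shown to be excluded.
- *Case-mix drift biases the comparison.* The basic analysis is paired, so stable patient characteristics cancel. The 15–20% turnover in section 5.4.1 concerns entrants and leavers. Calendar and seasonal drift is the part that stands.
- *A drift of 0.9 points is enough.* Session-level sampling error alone, with 36 and 72 sessions per patient, gives 1.96 × √(0.16 × (1/36 + 1/72) / 300) = 0.0092. That is a floor, because it leaves out variation between facilities and patients.

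**Conclusion.** The gap is real but limited to this secondary analysis. As written, the maintenance question is answered by within-group changes that carry any shared calendar or seasonal drift, and the contrast that would remove the drift is optional. That these estimates equal true change plus drift follows from the form of the tests and needs no assumption.

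The size does need assumptions. With the planning SD and ICC, and the assumed correlations above, drift of about 0.9 to 3.0 points (normal) or 1.3 to 4.2 points (t, 4 df) would reach significance in a group with no change in effect. Most of that range lies below the 3.4 to 4.3 points the trial is designed to detect. The documents do not say how large drift is likely to be, so these are illustrative ranges, not a forecast. The plan should be changed; the primary between-arm comparison is not affected.

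**What to change.** Make the joint analysis mandatory and define it as the maintenance analysis.

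- Fit one mixed model on all 20 facilities, with phase (baseline, weeks 1–24, each post-intervention month) crossed with the provider and patient-activation indicators.
- Include random effects for patient, facility and facility-by-phase, and use small-sample degrees of freedom suited to 20 clusters.
- Report the between-arm effect in weeks 25–36, as change from baseline, with its 95% confidence interval. Report also its difference from the weeks 1–24 effect with an interval. This settles which comparator defines maintenance.
- Keep the within-group changes as description only.

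The cost is SAP wording; the data and software stay the same. The downside is wider intervals: under the variance formula above, one group against control has an SE √2 = 1.41 times that of the within-group change. A 10-against-10 main-effect contrast brings the SE back to that of a single group's change, but it relies on the factorial assumption of no interaction.
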